6.2.1.2 Serious Adverse Events

An SAE is defined as any event that

- results in death
- is immediately life-threatening
- requires inpatient hospitalization or prolongation of existing hospitalization
- results in persistent or significant disability/incapacity
- is a congenital anomaly/birth defect

Adverse events will be assessed from the time the patient signs the ICF until exit from the study (ie, 52 weeks or end of treatment [ET] after Day 0 "rollover").

Serious AEs that occur more than 56 days (ie, 8 weeks) after the last dose of investigational study drug and the patient has exited the study need not be reported unless the investigator considers them related to investigational study drug.

At every study visit, patients will be asked a standard non-leading question to elicit any medically related changes in their well-being. They will also be asked if they have been hospitalized, had any accidents, used any new medications, or changed concomitant medication regimens (both prescription and over-the-counter medications).

In addition to patient observations, AEs identified from any study data (eg, laboratory values, physical examination findings, changes in 12-lead ECG results) or identified from review of other documents that are relevant to patient safety will be documented on the AE page in the eCRF.

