4.2 Withdrawal of Patients from the Study

Patients will be followed up for 52 weeks after they enter the ABP-19002 OLE study.

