4.2.1 Reasons for Withdrawal/Discontinuation

Patients may withdraw from the study at any time and for any reason without prejudice to their future medical care by the investigator or at the study site. Every effort should be made to keep patients in the study. The reasons for patients not completing the study will be recorded. A patient may be withdrawn from the study for any of the following reasons:

8. The patient withdraws consent.

The investigator will also withdraw a patient if Aeon Biopharma, Inc. terminates the study. Upon occurrence of a serious or intolerable AE, the investigator will confer with the sponsor. If a patient is discontinued because of an AE, the event will be followed until it is resolved. Any patient may withdraw his or her consent at any time.

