4.2.2 Handling of Withdrawals

Patients are free to withdraw from the study or study treatment at any time at their request. Patient participation in the study may be stopped at any time at the discretion of the investigator or at the request of the sponsor.

It is vital to obtain follow-up data on any patient withdrawn because of an AE or SAE. In every case, efforts must be made to undertake protocol-specified safety follow-up procedures. All data collected from all patients, including early withdrawals and early discontinuations of treatment, will be used in the reporting and analysis of the study.

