7.5.1 Analysis of Primary Estimand

The proportion of patients with treatment-related SAEs up to Week 52 will be summarized for the SASR.

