4.5.4. Safety Analysis Set with Retreatment (SAFR)

The SAFR will consist of all patients in the SAF but will exclude patients who do not receive more than one treatment of ABP-450 within the OLE study. The SAFR will be used for analysis of the primary estimand.

5. Patient Disposition

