8.1. Adverse Events

AEs will be collected from the time of signing of the ICF until 52 weeks or end of treatment after Day 1 "rollover" (exit from the study). All AEs will be classified by SOC and PT according to the MedDRA, version 24.0 or later.

Serious AEs that occur more than 56 days (i.e., 8 weeks) after the last dose of investigational study drug and the patient has exited the study may be reported if the investigator considers them related to investigational study drug.

[figure not shown]
The severity or intensity of an AE refers to the extent to which an AE affects the patient's daily activities. Adverse event severity will be classified as "Mild", "Moderate", and "Severe". TEAEs with missing severity will be imputed as 'Severe'.

The investigator will provide an assessment of the relationship of the event to the trial drug. The possible relationships are "Unrelated", "Possibly Related", "Probably Related" and "Definitely Related". Any TEAE reported as "Definitely Related", "Possibly Related" or "Probably Related" will be considered related to the ABP-450. TEAEs that are missing a relationship will be counted in the summary table as "Definitely Related" but will be presented in the data listing with a missing relationship.

Treatment emergent adverse events (TEAEs) are defined as those AEs that started on or after the day of first dose of ABP-450 up to 5 days after the end of treatment or end of study visits. Only TEAEs will be included in the AE summary tables. However, all adverse events will be listed and TEAEs will be flagged.

[figure not shown]
The TEAEs will be summarized by SOC and PT and will include the number and percentage of patients experiencing an event and the number of events (based on start date of the event) by treatment cycle and treatment group. Patients will be counted only once for each SOC and PT level (categorical descriptive analyses). In general, TEAE summary tables will be sorted by SOC and PT in descending order of frequency from the SOC and PT with the highest total frequency to the SOC and PT with the lowest total frequency.

For the purpose of inclusion in TEAE tables, incomplete AE onset and end dates will be imputed following date imputation guidelines (see Section 13.2).

[figure not shown]

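### The adverse event window ends at Week 52 or end of treatment, which conflicts with 52-week follow-up and a Week 52 primary proportion; a late related SAE could be listed but not counted

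*Protocol*

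**What the plan says.** **AE window.** The protocol's text on eliciting adverse events (under 6.2.1.2) assesses AEs from consent "until exit from the study (ie, 52 weeks or end of treatment [ET". SAP 8.1 agrees: "AEs will be collected from the time of signing of the ICF until 52 weeks or end of treatment", which it also equates with study exit.

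**Follow-up.** Protocol 4.2 states: "Patients will be followed up for 52 weeks after they enter the ABP-19002 OLE study". The synopsis and 6.1 say the same. None of them makes an exception for patients who stop injections.

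**Stopping treatment and leaving the study.** Protocol 4.2.2 treats these as two things: "Patients are free to withdraw from the study or study treatment at any time at their request". SAP 5.1 tabulates them separately. Protocol 11.3 defines the end of the study by the 52-week visit, patient withdrawal or discontinuation by the sponsor; end of treatment is not on that list.

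**Primary analysis.** Protocol 7.5.1: "The proportion of patients with treatment-related SAEs up to Week 52 will be summarized for the SASR". The set (SASR in the protocol, SAFR in the SAP) "will exclude patients who do not receive more than one treatment of ABP-450 within the OLE study".

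**Reporting after exit.** Protocol 6.2.1.2 releases the site from reporting an SAE only if it falls more than 56 days after the last dose and the patient has exited, and not if the investigator judges it related. SAP 8.1 describes the same late related SAEs as ones that may be reported, which is permissive where the protocol is not.

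**Tabulation.** SAP 8.1 closes the TEAE window 5 days after the end-of-treatment or end-of-study visit and admits only TEAEs to the AE summary tables. All AEs are listed.

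**The concern.** Take a patient treated twice in the OLE who declines further injections at Week 20 without withdrawing consent. Under protocol 4.2 the site follows this patient to Week 52. Under the AE text it may regard the patient as having exited at end of treatment, and the standard AE question, which is put at study visits, is no longer asked. The two readings differ by up to 52 − 20 = 32 weeks of scheduled questioning, and sites may choose differently.

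Two losses could follow. New non-serious AEs after end of treatment have no visible provision that keeps them under collection, although the primary objective is safety as a whole and SAP 8.1.10 tabulates non-serious events suggestive of distant toxin spread. Related SAEs stay reportable, but they then depend on spontaneous report, and the TEAE window can keep a reported one out of the tables. Any event missed or not counted lowers the proportion, so the error favours the product.

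**Working it through.** The plan has no power calculation or target rate to reproduce. Its sample size (about 60 in protocol 7.2, about 59 in SAP 4.3) is an enrolment forecast. The check has two parts.

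**1. The text, for the Week 20 patient**

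| Item | Where | Ends |
|---|---|---|
| Follow-up | Protocol synopsis, 4.2, 6.1 | Week 52 |
| Scheduled AE assessment | Protocol 6.2.1.2, SAP 8.1 | Week 52 or end of treatment |
| Related SAEs reportable | Protocol 6.2.1.2 | No time limit |
| Other SAEs reportable after exit | Protocol 6.2.1.2 | 56 days after last dose |
| TEAE tables | SAP 8.1 | 5 days after the end-of-treatment or end-of-study visit |
| Primary proportion | Protocol 7.5.1 | Week 52 |

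If the end-of-treatment visit falls at Week 20, a related SAE later in the year is reportable and inside the primary period, but outside the TEAE window.

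**2. Illustrative size**

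The documents give no discontinuation rate or event risk, so every input below except N = 60 is assumed: 52-week risk p, fraction d stopping early, constant hazard, stopping time T uniform over 52 weeks, and capture for w weeks after stopping.

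λ = −ln(1 − p)/52

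Crude proportion = (1 − d)·p + d·E[1 − exp(−λ·min(52, T + w))]

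For p = 5% and w = 0, 52λ = −ln(0.95) = 0.05129. The mean risk in a stopper is 1 − 0.05/0.05129 = 2.52%.

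- d = 10%: 0.9 × 5% + 0.1 × 2.52% = 4.75%
- d = 20%: 0.8 × 5% + 0.2 × 2.52% = 4.50%, and 60 × (5.0% − 4.50%) = 0.3 expected events missed
- d = 30%: 0.7 × 5% + 0.3 × 2.52% = 4.26%
- d = 40%: 0.6 × 5% + 0.4 × 2.52% = 4.01%

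With p = 5% and d = 20%, by capture after stopping:

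| Capture after stopping | Crude proportion | Relative loss |
|---|---|---|
| None | 4.50% | 9.9% |
| 5 days (TEAE window) | 4.52% | 9.6% |
| 8 weeks (56 days) | 4.65% | 7.1% |
| To Week 52 | 5.00% | 0 |

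Over p = 2–10% and d = 10–30% with no capture after stopping, the relative loss is about 5–15%, or 0.06 to 0.88 expected events among 60.

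With zero events, the upper limit of the two-sided 95% interval is 1 − 0.025^(1/60) = 6.0% for 60 fully observed patients. If d = 20%, person-time is 1 − 0.2 × 0.5 = 90% of full, which corresponds to 54 patients, and the limit is 1 − 0.025^(1/54) = 6.6%.

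The rows without capture to Week 52 are upper-end figures for their assumed rates. They let patients stop from Day 0, although those with one OLE treatment are not in the primary set. They also hold the hazard constant, although drug-related risk may fade after the last injection.

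**The case against.** A reader might infer that early stoppers are counted as event-free for time nobody observed, and that the primary result is biased by 10–20%. The documents do not support that.

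- The endpoint is treatment-related SAEs, the category that protocol 6.2.1.2 keeps reportable without time limit. Scheduled questioning may lapse; the reporting duty does not.
- It is tempting to say that only the AE behind a discontinuation is followed, from 4.2.1: "If a patient is discontinued because of an AE, the event will be followed until it is resolved". But 6.2.1.4 and 6.2.1.9 follow all recorded AEs to resolution or a stable state, and 4.2.2 asks for efforts at safety follow-up in every case.
- Patients who stop after one OLE treatment are excluded from the primary set, so they are not counted as event-free there.
- End of treatment may denote an exit visit. The protocol offers it as a gloss on study exit, and SAP 8.1 mentions an end-of-treatment visit. Nothing visible says that declining an injection triggers it, and the visit schedule is not shown.
- The primary estimand text (protocol 2.2.2 and 7.1, SAP 3.2.1 and 8.1.1) is not shown, so a rule for incomplete follow-up or late related SAEs cannot be excluded.
- The 10–20% comes only from assuming that 20–40% stop, at 0.5 × d of person-time.

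All of this stands, and it limits the point. It does not remove the conflict. The follow-up asked for in 4.2.2 consists of protocol-specified procedures, whose end date is the open question. Following recorded events does not find new ones. An estimand rule could not recover data never collected. The ambiguity about end of treatment is itself a reason to clarify.

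**Conclusion.** The point holds in limited form. The either/or end of AE assessment conflicts with 52-week follow-up, with the separation of stopping treatment from leaving the study, with the end-of-study definition in protocol 11.3 and with a primary proportion to Week 52. What can be lost, for patients who stop after two or more OLE treatments but stay in the study, is scheduled ascertainment and new non-serious AEs. One-treatment patients can lose the same in the general safety tables. In addition, a reported late related SAE could be listed but left out of the tables.

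The effect on the primary proportion is probably small and cannot be sized from the documents. At an assumed 5% risk with 20% stopping, it is at most about 4.5% against 5.0%, or 0.3 events among 60, and nil if related SAEs to Week 52 are all captured and counted. The change is worth making because it is cheap and removes an error that could only favour the product.

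**What to change.** 1. Reconcile protocol 4.2, 6.2.1.2 and 11.3 with SAP 8.1. State that AE and SAE collection runs to Week 52 unless consent is withdrawn, the patient dies or is lost to follow-up, using contacts already scheduled. Define end of treatment and say whether it means leaving the study.
2. Keep the protocol's rule on related SAEs after exit and make the SAP wording match it.
3. Align the TEAE window so that related SAEs up to Week 52 count in the primary proportion.
4. Report how many patients in the primary denominator were observed to Week 52.

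The cost is a few sentences across the two documents, plus continued contact with some patients who are off treatment, which the 52-week follow-up already implies. The change concerns data collection and counting only; no dosing or treatment-stopping rule changes.

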6.2.1.4 Reporting Adverse Events

All AEs reported or observed during the study will be recorded on the AE page in the eCRF. Information to be collected includes the following:

- Drug treatment
- Dose
- Event term
- Time of onset
- Investigator-specified assessment of severity and relationship to investigational study drug
- Time of resolution of the event
- Seriousness
- Any required treatment or evaluations
- Outcome

Adverse events resulting from concurrent illnesses, reactions to concurrent illnesses, reactions to concurrent medications, or progression of disease states must also be reported. All AEs will be followed to adequate resolution. The Medical Dictionary for Regulatory Activities (MedDRA) will be used to code all AEs.

Any medical condition that is present at the time that the patient is screened but does not deteriorate should not be reported as an AE. However, if it deteriorates at any time after Screening Visit, it should be recorded as an AE.

6.2.1.5 Reporting Serious Adverse Events

Sponsor or its designee is responsible for reporting relevant SAEs to the competent authority, other applicable regulatory authorities, and participating investigators, in accordance with the ICH guidelines and/or local regulatory requirements.

The sponsor is responsible for reporting unexpected fatal or life-threatening events associated with the use of investigational study drug (expedited reports) to the regulatory agencies and competent authorities by telephone or fax within 7 calendar days after being notified of the event. The sponsor should report other relevant SAEs associated with the use of investigational study drug to the appropriate competent authorities (according to local guidelines), investigators, and the institutional review board (IRB) by a written safety report within 15 calendar days of notification.

6.2.1.6 Suspected Unexpected Serious Adverse Reactions and Non-Serious Adverse Events of Special Interest

The sponsor will promptly evaluate all suspected unexpected serious adverse reactions (SUSARs) and non-serious AEs of special interest against cumulative investigational study drug experience to identify and expeditiously communicate possible new safety findings to investigators, IRBs/independent ethics committees (IECs), and applicable health authorities based on applicable legislation.

6.2.1.7 Assessment of Severity

The severity, or intensity, of an AE refers to the extent to which an AE affects the patient's daily activities. The intensity of the AE will be rated as mild, moderate, or severe using the following criteria:

Mild:	An event usually transient in nature and generally not interfering with normal
	activities.

Moderate: An AE that is sufficiently discomforting to interfere with normal activities.

Severe: An AE that is incapacitating and prevents normal activities.

Changes in the severity of an AE should be documented to allow an assessment of the duration of the event at each level of intensity to be performed. AEs characterized as intermittent do not require documentation of onset and duration of each episode.

6.2.1.8 Assessment of Causality

The investigator's assessment of an AE's relationship to investigational study drug is part of the documentation process, but it is not a factor in determining what is or is not reported in the study. If there is any doubt as to whether a clinical observation is an AE, the event should be reported.

The relationship or association of the test article in causing or contributing to the AE will be characterized using the following classification and criteria:

- Unrelated: This relationship suggests that there is no association between investigational study drug and the reported event.
- Possible: This relationship suggests that treatment with investigational study drug caused or contributed to the AE, ie, the event follows a reasonable temporal sequence from the time of drug administration or follows a known response pattern to investigational study drug but could also have been produced by other factors.

- Unrelated: This relationship suggests that there is no association between investigational study drug and the reported event.
- Probable: This relationship suggests that a reasonable temporal sequence of the event with drug administration exists and, based upon the known pharmacological action of the drug, known or previously reported adverse reactions to the drug or class of drugs, or judgment based on the investigator's clinical experience, the association of the event with investigational study drug seems likely. The event disappears or decreases on cessation or reduction of the dose of investigational study drug.
- Definite: This relationship suggests that a definite causal relationship exists between drug administration and the AE, and other conditions (concurrent illness, progression or expression of disease state, or concurrent medication reaction) do not appear to explain the event. The event reappears or worsens if the investigational study drug is re-administered.

6.2.1.9 Follow-Up of Patients Reporting Adverse Events

All AEs must be reported in detail on the appropriate page in the eCRF and followed to satisfactory resolution, until the investigator deems the event to be chronic or not clinically significant, or until the patient is considered to be stable.

	-

6.3 Secondary Efficacy Assessments

6.3.1 TWSTRS Scale

Most studies leading to the approval of currently available botulinum neurotoxins have used the TWSTRS scale as the primary efficacy measure (Fernandez 2013; Espay 2018). The standard TWSTRS is a comprehensive scale that comprises three subsets to assess motor severity, pain, and disability (Comella 2016). The motor severity subscale consists of 10 items, with variable scaling and weighting. It also includes a disability subscale with 7 items, and a pain scale with 3 items. The total score is the sum of each of the subscales.

6.3.2 PGI-C and CGI-C Scales

The PGI-C enables the patient to rate changes in their perception of their general health status over the duration of the assessment via a 7-point scale ranging from "very much improved" to "very much worse" (Fischer 1999). For this study, a 5-point generic PGI-C scale ranging from "much better" to "much worse" was used (FDA 2018). Similarly, the CGI-C is a 7-point scale ranging from "very much improved" to "very much worse" (Guy 1976) based on the physician's perception of the patient's health status. Detailed descriptions of the PGI-C and CGI-C are provided in Appendix 13.4 and Appendix 0, respectively.

6.3.4 C-SSRS

The C-SSRS was developed by the FDA in 2012 for measuring suicidal ideation and behavior in clinical trials (Posner 2011). The C-SSRS was designed to distinguish the domains of suicidal ideation and suicidal behavior. Four constructs are measured. The first is the severity of ideation (hereafter referred to as the "severity subscale"), which is rated on a 5-point ordinal scale in which 1=wish to be dead, 2=non-specific active suicidal thoughts, 3=suicidal thoughts with methods, 4=suicidal intent, and 5=suicidal intent with plan. The second is the intensity of ideation subscale (hereafter referred to as the "intensity subscale"), which comprises five items, each rated on a 5-point ordinal scale: frequency, duration, controllability, deterrents, and reason for ideation. The third is the "behavior subscale," which is rated on a nominal scale that includes actual, aborted, and interrupted attempts; preparatory behavior; and non-suicidal self-injurious behavior. The fourth is the "lethality subscale," which assesses actual attempts; actual lethality is rated on a 6-point ordinal scale,

and if actual lethality is zero, potential lethality of attempts is rated on a 3-point ordinal scale (Posner 2011). A detailed description is provided in Appendix 13.7.

6.3.5 Dysphagia Score

6.4 Safety Monitoring Committee

The medical monitor and sponsor will hold monthly reviews of all AEs; consequently, an independent Safety Committee will not be formed for this study.

6.5 Pregnancy

_
1
_

6.6 Laboratory Analyses

Any abnormal laboratory test results

including those that worsen from Day 0 "rollover," felt to be clinically

significant in the medical and scientific judgment of the investigator are to be recorded as AEs or SAEs.

However, any clinically significant safety assessments that are associated with the underlying disease, unless judged by the investigator to be more severe than expected for the patient's condition, are not to be reported as AEs or SAEs.

6.7 Sample Collections

Site personnel will collect blood samples at the visits specified in Section 6.1. These samples will be processed at the site and shipped same day to a central laboratory, as specified in the laboratory manual.

7 Statistical Considerations

This section briefly describes statistical and analytical methods to be used for the study. A statistical analysis plan (SAP) will provide details of the statistical methods and definitions for the analysis of efficacy and safety data. To preserve the integrity of the statistical analysis and study conclusions, the SAP will be finalized before database lock.

7.1 Estimands

7.2 Sample Size Calculations

All eligible patients who had their initial dose of study drug in the ABP-19000 studies, irrespective of treatment allocation, and consented to being treated with ABP-450 will be eligible to enroll in this OLE study.

Approximately 60 patients could enroll in this OLE study from the ABP-19000 study,

